12.4 Proportion of injection visits that occurred “on-time”

Population: Injection population

Analysis description: Number and percent of injection visits (up to 5 per participant) that occur “on-time”¹, using the number of injections given as the denominator. This will be presented along with the total number and percent of injections given, among all intended injections (i.e. 5 injections per participant).

¹The target injection date is defined by the W5 visit i.e. for the initial injection, the target injection date is 0 days (same day), and is +28, +84, +140, +196 days from the W5 visit for injections 2-5, respectively. The target visit window for injection visits for the week 5 injection is 0 to 3 days after the W5 visit (if the injection could not be done on the same day as the W5 visit), for all other injection visits (W9, W17, W25, W33) the target window is +/-3 days from the target injection date. Injection dates happening within the target window are considered “on-time”.

12.5 Change from enrollment of self-reported sexual behavior (number of sexual partners, and number of episodes of anal intercourse without a condom) during the study period

Note: This secondary analysis will not be included in the Clinical Study Report.

Population: Enrolled population

Analysis description: Counts of sexual partners and episodes of anal intercourse without a condom will be summarized (mean and median) at enrollment and each regular Step 1 and Step 2 follow-up visit (W4, W5, W9, W17, W25, W33, +8).

12.6 Evaluate rates of HIV drug resistance among participants who acquire HIV infection during the study

Population: Seroconverter population

Analysis description: Data from steps 1, 2, and 3 will be included. The number of cases of drug resistance will be summarized. All cases of drug resistance among incident HIV infections will be described.

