### **2.2 Secondary Objectives**

- To examine adherence to and timeliness of injections over time among adolescent participants who are provided CAB LA and information regarding its safety and unknown efficacy.
- To examine patterns of sexual risk behavior over time among adolescent participants who are provided CAB LA and information regarding its safety and unknown efficacy.
- To evaluate the safety of CAB LA for 48 weeks of follow-up after final injection.
- To characterize the pharmacokinetics of CAB LA.

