## **5.9 Injection Visit Windows**

The visit windows for all visits, including injection visits, are outlined in the SSP Manual. Refer to SSP for instruction on managing participants who report to clinic outside of injection window.

The target visit windows for all visits, including injection visits, are outlined in the SSP Manual. In brief, the target visit window for all injection visits is +/- 3 days. Visits conducted outside of the target visit windows are allowable without restriction and are also defined in the SSP Manual for scheduling guidance. Each study visit, including the injection visit, should ideally be conducted within the target date range. When that is not possible, visits outside of the target dates may be completed.

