Acceptability endpoints: Proportion of participants who complete all scheduled injections and proportion of participants who receive at least one injection who would consider using CAB LA for HIV prevention in the future. This endpoint will be evaluated using CASI questionnaires at the last injection visit (Step 2, week 33) for participants who do not have acceptability data at the Step 2, week 33 visit (either due to a change in when the questionnaire items were administered², missed the final injection visit, or discontinue injections early) and continue to step 3, acceptability endpoints are evaluated during the follow up phase (step 3, week +12). The primary acceptability outcome is:

If you wanted to protect yourself from getting HIV, which of the following product(s) would you prefer to use?

- Prefer not using a product
- Condoms only
- Oral PrEP pills only
- Injectable PrEP only
- Condoms and oral PrEP pills together
- Condoms and injectable PrEP together
- Prefer not to answer

Secondary endpoints:

- Proportion of injection visits that occurred “on-time”
 - The target visit window for the week 5 injection is 0-3 days after the Week 5 visit date (allowing for the injection occurring on a different day from the W5 visit) and is +/-3 days from the target injection date for all other injection visits. Visits happening within the target window are considered “on-time”
- Change from enrollment of self-reported sexual behavior (number of sexual partners, increased episodes of anal sex without a condom) during the study period
- Proportion of participants experiencing Grade 2 or higher clinical AEs and laboratory abnormalities in the oral phase and the aggregate over the entire study period
- Plasma CAB pharmacokinetics

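### The on-time figure gives injection 1 a nearly automatic success and pools all injections, so the planned summary cannot show timeliness over time

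*SAP*

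**What the plan says.** SAP 12.4 analyses on-time injections in the Injection population. The "target injection date is defined by the W5 visit", and the "window for injection visits for the week 5 injection is 0 to 3 days after the W5 visit". SAP 2.2 gives the same rule, "allowing for the injection occurring on a different day from the W5 visit". Targets for the later injections are plus "28, +84, +140, +196 days from the W5 visit for injections 2-5", and for these "the target window is +/-3 days from the target injection date".

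The percentage pools up to five injections per participant, "using the number of injections given as the denominator". Beside it, SAP 12.4 presents injections given as a share of five intended per participant. The opening of SAP 12 plans each summary overall and by site, and overall only for the Clinical Study Report. No summary by injection number or visit is planned.

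The objective in Protocol 2.2 begins "To examine adherence to and timeliness of injections over time among adolescent participants", and SAP 2.2 repeats it. Protocol 5.9 says that "the target visit window for all injection visits is +/- 3 days" and refers to the SSP Manual for the windows in full. Protocol 7.8.4 asks for one number and one percentage.

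**The concern.** Two features combine.

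- **Injection 1 is scored against a date that moves with it.** If the Week 5 visit is late and the injection is given that day, the delay is zero by definition. The later targets are counted from the same visit, so the delay never appears afterwards either.
- **The five injections are merged into one percentage.** A decline from the first to the fifth injection and a steady moderate rate can give the same figure.

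The objective asks how timeliness behaves over time, and the planned summary has no time axis. SAP 12.5, the next secondary analysis that serves an over-time objective, does summarise its outcome visit by visit.

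**Working it through.** **1. The plan's own target days.** The scheduled injection weeks are 5, 9, 17, 25 and 33 (Protocol 2.3). Days from Week 5 = 7 × (week − 5), which gives 0, 28, 84, 140 and 196. These match SAP 12.4 exactly.

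**2. How the rule scores three constructed participants.**

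- *Late Week 5 visit.* The visit is 20 days later than enrollment + 35 days, the injection is given the same day, and all later intervals are exact. The SAP score is 5 of 5. On a calendar counted from enrollment (days 35, 63, 119, 175, 231) it would be 0 of 5. This shows what the figure cannot see. It does not show that the enrollment calendar is the right standard.
- *First injection held.* Injection 1 is given 5 days after the Week 5 visit. The SAP counts it as late, so success at injection 1 is not guaranteed.
- *One later delay.* Injection 2 is 10 days late and each later interval is exactly 56 days. Injections 2 to 5 each fall 10 days after their fixed target, so the SAP score is 1 of 5. Judged from the previous injection, the score is 4 of 5.

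**3. What injection 1 adds to the pooled figure.** Let p be the on-time rate for injections 2 to 5 and m the mean number of injections given per participant. If injection 1 is always on time,

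pooled = (1 + (m − 1)p) / m, and pooled − p = (1 − p) / m.

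The documents give neither p nor m. The values below are assumptions.

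| p | pooled, m = 5 | excess, m = 5 | excess, m = 3 |
|---|---|---|---|
| 0.5 | 0.60 | 10 points | 16.7 points |
| 0.6 | 0.68 | 8 points | 13.3 points |
| 0.7 | 0.76 | 6 points | 10.0 points |
| 0.8 | 0.84 | 4 points | 6.7 points |
| 0.9 | 0.92 | 2 points | 3.3 points |

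**4. What pooling hides.** SAP 6.4 reports that enrollment stopped at nine, so there are at most 9 × 5 = 45 Step 2 injections. Take two illustrative sets of on-time counts, each out of nine, for injections 1 to 5:

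- 9, 9, 8, 6, 4: a fall from 100% to 44%.
- 9, 7, 6, 7, 7: roughly level after the first.

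Both sum to 36, so both report 36/45 = 80%. Without injection 1 both give 27/36 = 75%. Removing injection 1 alone therefore does not reveal the trend. Only the breakdown by injection number does.

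**5. The denominator.** Assume 9, 8, 7, 6 and 5 participants receive injections 1 to 5, so 35 of 45 are given, with p = 0.8 and injection 1 always on time. On-time injections = 9 + 0.8 × 26 = 29.8. That is 29.8/35 = 85.1% of those given and 29.8/45 = 66.2% of those intended. SAP 12.4 would print 85.1% with 35/45 = 77.8% beside it. The product of the two is 66.2%, so a reader can recover the overall shortfall, but not the injection at which it arose.

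**The case against.** The strongest case for the plan has five parts.

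- **The SAP follows the protocol.** Protocol 7.2.2 defines the endpoint as a proportion of injection visits, and 7.8.4 asks for one count and percentage. This is correct. The gap lies between the objective and the endpoint, and both documents share it.
- **Drop-off is not concealed.** A reader might infer that participants who stop early vanish from view. They do not. Injections given over intended stands beside the on-time percentage, completion of all scheduled injections is a primary endpoint (SAP 8.3.1), and discontinuation for intolerance or burden is another (SAP 8.2). What stays unseen is the timing of missed injections within this endpoint.
- **The Week 5 anchor is defensible.** It preserves the scheduled spacing. A reader might infer that it contradicts Protocol 5.9 and that injection 1 should be scored against enrollment + 35 days. Section 5.9 gives a window width and names no such anchor. The first injection may also be held for reasons that the protocol itself imposes, such as a repeat ALT after a Grade 2 result at Week 4 (Table 5.1 and Appendix VI). Scoring against enrollment could record those holds as lateness.
- **The bias is not all one way.** A reader might infer that the endpoint overstates punctuality as a whole. The third case in step 2 shows that the fixed anchor can understate it, so the upward effect is established only for the contribution of injection 1.
- **A decline over time is not documented.** Protocol 1.1 reports protective adherence falling from 54% to 22% in an adolescent study, but that concerned daily oral pills. It is not evidence that injection punctuality falls.

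A table by injection number will also be imprecise with nine enrolled: 4 of 9 has an exact 95% confidence interval of 14% to 79%. That limits the table to description. It does not remove the reason for showing it.

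**Conclusion.** The point holds in a limited form. Injection 1 is a nearly automatic success, because lateness of the Week 5 visit can never count against it. The planned pooled summary, overall or by site, cannot show timeliness over time. The data could, since the analysis already needs each injection date.

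The contribution of injection 1 is (1 − p)/m. For a full course this is 2 to 10 points as p goes from 90% to 50%, and more if fewer injections are given. The range rests on assumed values of p and on injection 1 always being on time, which the SAP rule makes likely but does not guarantee.

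The documents do not support calling the first injection punctual by construction, the whole endpoint biased upward, or attrition hidden. This is an inexpensive improvement in reporting and does not invalidate the endpoint.

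**What to change.** In SAP 12.4:

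1. Tabulate by injection number (W5, W9, W17, W25, W33) the number on time and the number given, each with the Injection population as denominator.
2. Report the pooled on-time percentage twice: with injection 1, and for injections 2 to 5 only.
3. Describe days from enrollment to the first injection as a separate summary. Do not rescore injection 1 against enrollment + 35 days.

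The cost is a few lines of SAP text and one descriptive table. It uses the injection and Week 5 dates that the analysis already needs, plus the enrollment date. The figure for injections 2 to 5 will probably be slightly lower than the pooled one. With nine enrolled, the by-injection rows should be presented as counts, without claims about trend.

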### **7.2.2 Secondary Endpoints**

- Plasma CAB pharmacokinetics
- Proportion of participants experiencing Grade 2 or higher clinical AEs and laboratory abnormalities in the oral phase and the aggregate over the entire study period
- Proportion of injection visits that occurred “on-time”
- Change from enrollment of self-reported sexual behavior (number of sexual partners, increased episodes of unprotected anal intercourse) during the study period

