### 7.8.5 Sexual Risk Behaviors

Change in sexual risk behavior (number of sexual partners, episodes of unprotected anal and/or vaginal intercourse) during the injection phase will be measured by summarizing the change from baseline by visit.

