## 12.3 APPENDIX III. SCHEDULE OF EVALUATIONS –FOLLOW-UP PHASE (STEP 3-ORAL PrEP)

WEEKS SINCE LAST INJECTION	Wk +8	Wk +12	Wk +24	Wk +36	Wk +48	Early Discontinuation
ADMINISTRATIVE, BEHAVIORAL, REGULATORY						
Locator information	X	X	X	X	X	X
HIV prevention & risk reduction counseling	X	X	X	X	X	X
Condoms per local SOC	X	X	X	X	X	X
Behavioral/Acceptability assessment (CASI)		X	X	X	X	X
CLINICAL EVALUATIONS & PROCEDURES						
Qualitative interviews continue (approximately)		X	X			
Medical history  , concomitant medications, targeted physical exam		X	X	X	X	
Hep B vaccination (if needed) 						X
Blood collection	X	X	X	X	X	
Urine collection			X		X	X
Rectal swab collection			X		X	
Provision of Tenofovir/Emtricitabine (Trade name: TDF/FTC, Truvada®) (3 months' worth)		X	X	X		X
LOCAL LABORATORY EVALUATIONS & PROCEDURES						
HIV testing 		X	X	X	X	
CBC with differential			X		X	X
Chemistry testing 		X	X	X	X	X
Liver function testing 		X	X	X	X	X
Syphilis testing			X			X
GC/CT testing (urine, rectal, and oral pharyngeal swabs)			X		X	
Urinalysis (protein, glucose; at the clinic or local lab)			X		X	X
Plasma storage 	X	X	X	X	X	
DBS storage		X	X		X	
HBsAb and HBcAb 					X	X
HCVAb					X	X

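### SAP 12.5 summarises sexual-behaviour counts visit by visit instead of the change from enrollment that defines the endpoint, and lists +8, a Step 3 visit with no CASI scheduled

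*SAP*

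**What the plan says.** Three places define the endpoint as a change. Protocol 7.2.2 has "Change from enrollment of self-reported sexual behavior (number of sexual partners, increased episodes of unprotected anal intercourse) during the study period". SAP 2.2 has "Change from enrollment of self-reported sexual behavior (number of sexual partners, increased episodes of anal sex without a condom) during the study period". The heading of SAP 12.5 repeats the idea. Protocol 7.8.5 gives the matching analysis, limited in time: behaviour "during the injection phase will be measured by summarizing the change from baseline by visit".

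The analysis description in SAP 12.5, for the Enrolled population, is different: "Counts of sexual partners and episodes of anal intercourse without a condom will be summarized (mean and median) at enrollment" and at follow-up visits that it assigns to Steps 1 and 2, namely "W4, W5, W9, W17, W25, W33, +8". It mentions no change variable, no pairing with the enrollment value and no count of pairs. SAP 12.5 also states that this analysis will not appear in the Clinical Study Report.

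On data collection, Protocol 5.14 lists sexual risk behaviour among the behavioural assessment areas. Protocol 5.2 puts all behavioural measures except the PHQ-9 into CASI. The schedules in Appendices I to IV show when CASI is given. Protocol 5.7 describes +8 as the visit that opens Step 3, held for a blood draw to complete CAB level monitoring.

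**The concern.** The endpoint asks how each participant's reported behaviour moved relative to enrollment. The planned summary describes the level of the group at each visit. The two agree only under conditions that the plan does not secure.

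The membership of the group can change. SAP 12.5 starts from everyone enrolled, but under Protocol 5.4.1 those who do not enter Step 2 leave follow-up. Under Protocol 5.7, those who miss the Week 33 injection are followed on the Step 3 schedule, counted from their last injection. Such participants count at enrollment and not at later Week-numbered visits. Leaving also need not be independent of behaviour, since one condition in Protocol 5.4 that could bar entry to Step 2 (subject to committee determination) concerns HIV risk itself. With nine people, one or two departures can drive a mean.

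The listing of +8 is a separate slip. A table built to SAP 12.5 would contain a visit for which the protocol schedules no questionnaire.

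**Working it through.** No stated figure of the plan is at issue, so the check is a comparison of passages plus arithmetic on assumed data.

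**Visits in SAP 12.5 against the CASI rows**

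| Visit in SAP 12.5 | Schedule | CASI marked? |
|---|---|---|
| W4 | Appendix I | yes |
| W5, W9, W17, W25, W33 | Appendix II | yes, all five |
| +8 | Appendix III (oral PrEP) | no; first at +12 |
| +8 | Appendix IV (injection) | no; first at +16 |

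So 6 of the 7 listed follow-up visits have a scheduled CASI, and +8 has none under either Step 3 option. The row, "Behavioral/Acceptability assessment (CASI"), is also marked at Early Discontinuation, but that is a different visit. SAP 12.5 groups +8 with Steps 1 and 2; Protocol 5.7 places it in Step 3. For comparison, SAP 2.2 uses week +12, not +8, as the fallback for missing Week 33 acceptability answers.

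**Do visit summaries recover the change?** All counts below are assumed; the documents give no partner counts.

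*Departures only.* Enrollment counts 0, 1, 1, 1, 2, 2, 3, 6, 10.
- Mean = 26/9 = 2.89; median = 2.
- The two highest leave and nobody changes: mean = (26 − 16)/7 = 10/7 = 1.43; median = 1.
- Apparent fall in the mean = 1 − 1.43/2.89 = 51%. The within-person change among the seven who stay is 0.

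*Departures plus change.* Enrollment 0, 1, 1, 2, 2, 3, 4, 6, 10 (mean 29/9 = 3.22). The two highest are missing later, and the other seven report 2, 1, 3, 0, 2, 1, 5 (mean 14/7 = 2.00).
- Difference of visit means = 2.00 − 3.22 = −1.22.
- Paired changes = 2, 0, 2, −2, 0, −2, 1; mean = 1/7 = +0.14. The sign is reversed.

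*Complete data.* The mean change always equals the difference of means. Medians carry no such guarantee. Take the first nine counts and let the later values, in the same participant order, be 1, 1, 1, 2, 2, 3, 6, 10, 0.
- Both visits have median 2, so the difference of medians is 0.
- Changes = 1, 0, 0, 1, 0, 1, 3, 4, −10; median change = 1.

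The median is one of the two statistics SAP 12.5 names, so this applies even if nobody is lost.

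**The case against.** The strongest reply is that SAP 12.5 keeps change from enrollment in its heading, that SAP section 12 refers the reader to 2.2 for endpoint definitions, and that levels at enrollment and each visit let a reader see movement. The secondary objective asks only for patterns of risk behaviour over time, which visit summaries do describe. This stands in part. It would be wrong to infer that the objective goes unanswered; what is missing is the endpoint's change measure. The heading names that measure but supplies no method, whereas SAP 9.2 states change from baseline explicitly for laboratory values.

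A reader might also infer that SAP 12.5 wrongly discards the later Step 3 questionnaires. The documents do not support that. Protocol 7.8.5 confines the analysis to the injection phase, and apart from +8 the visit list in SAP 12.5 ends with Step 2. Protocol 5.5 and 5.7 also say that CASI at these visits may carry behavioural or acceptability items, so a mark in the schedule does not prove that partner counts or condomless episodes were asked. What is real is a conflict of scope between the study period in the endpoint and the injection phase in 7.8.5.

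For the same reason one cannot say that the +8 column is certain to be empty. A SAP 2.2 note on acceptability refers to a change in when items were administered. The documents show only that no CASI is scheduled at +8.

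Individual trajectories and a split by Step 3 product are reporting preferences. With nine participants enrolled as minors at three sites, listings carry a confidentiality cost, and the product groups would be tiny and could change, since switching to CAB LA is allowed.

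**Conclusion.** Two points hold. The analysis text of SAP 12.5 does not carry out the change from enrollment named in its own heading, in SAP 2.2 and in Protocol 7.2.2, and planned in Protocol 7.8.5. It also lists a Step 3 visit with no scheduled CASI among the Step 1 and Step 2 visits.

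The consequence is modest: a descriptive secondary analysis with no test or decision rule, excluded from the Clinical Study Report, in a study whose accrual stopped at nine (SAP 6.4). The 51% fall and the reversed sign show that the problem can arise. They are not estimates for this trial, because they assume both the counts and that the highest reporters leave. SAP 12.5 does not say how missing visits are handled, so the reading that each visit summary uses whoever has data is an inference, though the natural one. The point about medians needs no assumption about attrition.

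**What to change.** - In SAP 12.5, add the within-person change from enrollment at W4, W5, W9, W17, W25 and W33: mean, median, range and number of participants with both values. Keep the visit levels beside it.
- Delete +8, or replace it with a visit at which the sexual-behaviour items were asked.
- Reconcile the period: whole study (Protocol 7.2.2, SAP 2.2, heading of SAP 12.5) or injection phase (Protocol 7.8.5). Add Step 3 CASI visits only if the wider scope is chosen and the items were administered there.
- Confirm from the questionnaire, visit by visit, where those items appear.

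The cost is a few lines of SAP text, one derived variable per count and a check of the instrument. No new data collection is needed for the Step 1 and Step 2 visits, provided that check confirms the items were asked.

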13 CHANGE HISTORY

Version		Affected Section(s)	Activity Description
Number	Effective Date		
1.0	02/20/2021	All sections	First version of SAP was developed.
2.0	Date of last signature	2, 3, 6, 7-9, 11, 12, 13, 16, 17	Revisions based on new option to continue CAB injections during Step 3. Added study populations and definitions. Updated consort diagram, primary and secondary outcomes/analyses, including addition of secondary outcome 12.6. Updated acceptability endpoint definition, and reference to PK analysis plan. Additional details to account for changes to schedule of visits and data collection, due to new CAB option in Step 3. Added sections: 13 (ad hoc analysis), appendices A, B and C (AEs of special interest, variable definitions and imputation of missing data). Most revisions are designed to harmonize with HPTN 084-01 SAP 3.0.

14. APPENDIX A – Adverse Events of Special Interest

Adverse events of special interest (AESI) have been determined for CAB based on pre-clinical and clinical experience, along with information for the integrase inhibitor class of HIV medications safety profile. These are adverse events for which more detailed summaries of event characteristics are of interest.

The identification and classification of AESI will be based on MedDRA preferred terms as specified in the ADRG (Analysis Data Reviewers Guide). The current MedDRA version used for the preferred terms in the ADRG is v25.1. Preferred terms will be updated in the ADRG if a new version becomes available before the database lock.

Table 1 below shows the adverse events of special interest identified and reasons for including.

Table 1 Adverse Events of Special Interest (Clinical Study Report only)

AESI	Product Implicated	Reason for Including as AESI
Hepatic Safety Profile: Assessment of risk of hepatotoxicity	CAB	Clinical, Class, Regulatory Interest,
Hypersensitivity Reactions (HSR)	CAB	Class, Regulatory Interest,
Rash	CAB	Class, Regulatory Interest
Neuropsychiatric Events 
 • Suicidal Ideation/Behavior • Depression • Bipolar Disorder • Psychosis • Mood Disorders • Anxiety • Sleep Disorders 	CAB	Clinical, Class, Regulatory Interest,
Injection Site Reactions (ISR)	CAB	Clinical, Regulatory Interest
Seizures and Seizure-like events	CAB	Clinical, Regulatory Interest
Weight Gain	CAB	Clinical, Class, Regulatory Interest
Rhabdomyolysis	CAB	Clinical, Class, Regulatory Interest
Pancreatitis	CAB	Clinical, Therapeutic Area, Regulatory Interest
Impact on Creatinine	CAB	Regulatory Interest, Therapeutic Area

Confidential

All proprietary rights reserved

Page 22 of 27

Hyperglycemia/new onset diabetes mellitus	CAB	Observation from 083, Class
---	-----	-----------------------------

Common ISR adverse events are defined by MedDRA preferred terms including injection site pain, injection site induration, injection site nodules and preferred terms of any other ISR exceeding the threshold as specified in the ADRG. ISRs will be explored regardless of IP relationship.

Each one of the AESIs described in Table 3 will be explored via the data listings in more detail. Listings will summarize Adverse events that occurred during Step 1 and/or Step 2 of the study and will contain information to assess the following.

Event Characteristics: The characteristics of all event occurrences during the post-baseline period will look at event characteristics (serious, drug-related, leading to withdrawal, or Grade 3/4, fatal), number of events per participant, outcome, maximum grade or intensity and action taken.

Time to First Event (TTFE) and Duration of Events: Time of onset and duration of event will be provided.

In addition, Pyrexia Plus includes PT: (Chills – 10008531, Feeling of Body Temperature Change - 10061458, Feeling Hot - 10016334, Body Temperature Increased - 10005911, Pyrexia - 10037660, Influenza Like Illness - 10022004, Fever – 10016558) events will be looked at in relation to timing of previous injection.

No formal summaries or statistical comparisons are planned for AESI.

15. APPENDIX B – Variable Definitions

1. CES-D-10 (score/categories)

Create a score based on 10 items below (in CASI questionnaire):

In the list below, please indicate how often you have felt this way during the past week by ticking the appropriate box for each question:

1. I was bothered by things that usually don't bother me.
2. I had trouble keeping my mind on what I was doing.
3. I felt depressed.
4. I felt that everything I did was an effort.
5. I felt hopeful about the future.
6. I felt fearful or afraid.
7. My sleep was restless.
8. I was happy.
9. I felt lonely.
10. I could not "get going", I did not feel motivated.

Scoring:

	Rarely or none of the time (less than 1 day)	Some or a little of the time (1-2 days)	Occasionally or a moderate amount of time (3-4 days)	All of the time (5-7 days)
--	--	---	--	----------------------------

Questions 5 & 8	3	2	1	0
All other questions	0	1	2	3

The total score is calculated by finding the sum of 10 items. Score as 'missing' if 1 or more items are missing/prefer not to answer. Any score ≥ 10 is considered depressed.

2. PHQ-9 (score/categories)

Create a score based on values from 9 questions (Not at all = 0, Several days = 1, More than half the days = 2, Nearly every day = 3):

Over the last 2 weeks, how often have you been bothered by the following problems?

1. Little interest or pleasure in doing things
2. Feeling down, depressed, or hopeless
3. Trouble falling or staying asleep, or sleeping too much
4. Feeling tired or having little energy
5. Poor appetite or overeating
6. Feeling bad about yourself - or that you are a failure or have let yourself or your family down",
7. Trouble concentrating on things, such as reading the newspaper or watching television",
8. Moving or speaking so slowly that other people could have noticed. Or the opposite - being so fidgety or restless that you have been moving around a lot more than usual
9. Thoughts that you would be better off dead, or of hurting yourself

PHQ-9 score obtained by adding score for each question (total points). Score as 'missing' if 1 or more items are missing. Then categories of depression severity are created from the total score according to: 0-4: None-minimal, 5-9: Mild, 10-14: Moderate, 15-19: Moderately Severe 20 – 27: Severe.

3. PC-PTSD-4 (score/categories)

Create a score based on values from 4 questions (yes = 1, no = 0):

In your life, have you ever had any experience that was so frightening, horrible, or upsetting that, in the past month, you:

1. Have had nightmares about it or thought about it when you did not want to?
2. Tried hard not to think about it or went out of your way to avoid situations that reminded you of it?
3. Were constantly on guard, watchful, or easily frightened?
4. Felt empty, numb or detached from others, activities, or your surroundings?

If missing or prefer not to answer any questions, then code score as missing. For non-missing scores, a score of 0-2 fails to indicate PTSD, and ≥ 3 indicates the potential for PTSD, which can be determined by a clinical interview.

4. Age-standardized BMI z-score

Based on World Health Organization (WHO) tool:

(1) <https://www.who.int/tools/growth-reference-data-for-5to19-years/indicators/bmi-for-age>

With instructions for calculations (see section “**Computation of centiles and z-scores**”, link to pdf: “**instructions in English**”):

(2) https://cdn.who.int/media/docs/default-source/child-growth/growth-reference-5-19-years/computation.pdf?sfvrsn=c2ff6a95_4

Age-specific values of necessary parameters $L(t)$, $M(t)$, and $S(t)$ can be downloaded from the website (1) (see section: “**Expanded tables for constructing national health cards**” link to dataset “**z-scores: girls**”)

Categorical BMI classification based on age-standardized BMI z-score as follows:

- Obesity: $>+2$
- Overweight: $>+1$ and $\leq+2$
- Normal: >-2 and $\leq+1$
- Thinness: >-3 and ≤-2
- Severe thinness: ≤-3

16. APPENDIX C – Imputation of missing dates

Missing Start and Stop Dates for Prior and Concomitant Medication, and Medical History

The Assumption is to consider the most conservative judgment when imputing.

Start date:

When imputing a start date ensure that the new imputed date is sensible i.e. is prior to the end date and the general rules are:

1. If start date is completely missing, start date will not be imputed
2. If year and month are present and day is missing, set day to the 1st day of month.
3. If year and day are present and month is missing, then set month to January.
4. If year is present and month and day are missing, set month and day to January 1st.

Stop date:

1. If end date is completely missing, end date will not be imputed
2. If year and month are present and day is missing, set day to the last day of month.
3. If year and day are present and month is missing, set month to December
4. If year is present and month and day are missing, set month and day to December 31st.

Missing Start and Stop Dates for Adverse Events (including ISRs)

The Assumption is to consider the most conservative judgment when imputing.

Start date:

1. If start date is completely missing, start date is set to date of first dose.
2. If (year is present, and month and day are missing) or (year and day are present, and month is missing):
 - a. If year = year of first dose, then set month and day to month and day of first dose.
 - b. If year < year of first dose, then set month and day to December 31st.
 - c. If year > year of first dose, then set month and day to January 1st.
3. If month and year are present and day is missing:
 - a. If year = year of first dose and
 - i. If month = month of first dose, then set day to day of first dose date.
 - ii. If month < month of first dose, then set day to last day of month.
 - iii. If month > month of first dose, then set day to 1st day of month.
 - b. If year < year of first dose, then set day to last day of month.
 - c. If year > year of first dose, then set day to 1st day of month.

Stop date:

If the outcome of the AE was ongoing or unknown, then the rules outlined below will not be applied.

1. If stop date is completely missing, stop date is set to date of study discontinuation.
2. If (year is present, and month and day are missing) or (year and day are present, and month is missing):
 - a. If year = year of study discontinuation, then set month and day to month and day of study discontinuation.
 - b. If year < year of study discontinuation, then set month and day to December 31st.
 - c. If year > year of study discontinuation, then set month and day to December 31st.
3. If month and year are present and day is missing:
 - a. If year = year of study discontinuation and
 - i. If month = month of study discontinuation, then set day to day of study discontinuation date
 - ii. If month < month of study discontinuation, then set day to last day of month.
 - iii. If month > month of study discontinuation, then set day to last day of month.
 - b. If year < year of study discontinuation, then set day to last day of month.
 - c. If year > year of study discontinuation, then set day to last day of month.

Missing Start and Stop Dates for Protocol Deviations

The Assumption is to consider the most conservative judgment when imputing.

Start date:

When imputing a start date ensure that the new imputed date is sensible i.e. is prior to the end date and the general rules are:

1. If start date is completely missing, start date will not be imputed
2. If (year is present, and month and day are missing) or (year and day are present, and month is missing), set month and day to January 1st.
3. If year and month are present and day is missing, set day to the 1st day of month.

Stop date:

1. If end date is completely missing, end date will not be imputed
2. If (year is present, and month and day are missing) or (year and day are present, and month is missing), set month and day to December 31st.
3. If year and month are present and day is missing, set day to the last day of month.

Approved

Signature Page for SCHARP-TMF-32741 v2.0

Reason for signing: Approved	Name: [name] Role: Data Analytics Date of signature: 17-Jan-2023 19:54:18 GMT+0000
------------------------------	--

Reason for signing: Approved	Name: [name] Role: Hutch SDMC Date of signature: 17-Jan-2023 23:02:14 GMT+0000
